**Single Agent Nirogacestat**

Dose-DLT data for nirogacestat as presented in Table 11 of the first-in-patient, dose-finding Phase 1 study (Messersmith et al 2015) are used to derive the prior of the single agent logistic parameters for nirogacestat.

090177e1a0f4f44c\Approved\Approved On: 14-Jun-2024 22:12 (GMT)

**Table 11. Historical Dose Limiting Toxicity Data on Nirogacestat**

Nirogacestat Dose Level (mg; BID)	Number of Participants	Number of Participants with DLTs
20	3	0
40	3	0
80	3	0
100	6	1
130	3	0
150	6	1
220	6	1
330	2	2

Abbreviations: BID=twice daily; DLT=dose limiting toxicity; mg=milligrams.

CCI [REDACTED] Priors for  $t_{1n}$  and  $t_{2n}$  are assigned such that (1) their medians correspond to moderate between-trial heterogeneity, and (2) their uncertainty (95% prior interval) cover plausible between-trial standard deviations.

CCI [REDACTED]

The prior distributions for the model used for deriving the MAP priors are specified in Table 12.

**Table 12. Prior Distributions for the Parameters of the MAP Model Used to Derive the Prior** CCI [REDACTED]

Parameter	Prior distribution
$\mu_{1n}$	N (mean = 0, sd = 2)
$\mu_{2n}$	N (mean = 0, sd=1)
CCI [REDACTED]	
$r_n$	Uniform (-1,1)

Abbreviations: N=normally distributed; sd=standard deviation.

090177e1a0f4f44c\Approved\Approved On: 14-Jun-2024 22:12 (GMT)

**Prior Distribution for the Interaction Parameter**

Based on pharmacometrics assessment the drug-drug interaction between elranatamab and nirogacestat is expected to be low, although uncertainty remains. CCI

The prior for  $\eta_{12}$  is specified as percentiles of increase in the odds of DLT due to possible interaction in combination therapy at reference doses:

CCI

**Summary of Prior Distributions**

The prior distributions of the model parameters are provided in Table 13. Table 14 illustrates the resulting prior distribution of DLT rate derived from the priors given in Table 13. Based on the available information, the starting dose elranatamab = 4 mg satisfies the EWOC criterion.

**Table 13. Prior Distribution for the Model Parameters in Nirogacestat BID model**

Parameter	Mean	Standard deviations	Correlation
Elranatamab single agent parameters: CCI			
$(\log(\alpha_1), \log(\beta_1))$	CCI		
Nirogacestat single agent parameters: CCI			
$(\log(\alpha_2), \log(\beta_2))$	CCI		
Interaction parameter: Normal prior			
$\eta_{12}$	CCI		

$\eta_{12}$ : Two-way interaction between elranatamab and nirogacestat.

Abbreviations: CCI

090177e1a0f4f44c\Approved\Approved On: 14-Jun-2024 22:12 (GMT)

**Table 14. Summary of Prior Distribution of Dose Limiting Toxicity Rates for CCI**

CCI	Prior Probabilities that DLT Rate is Within the Interval			Mean	SD	Quantiles		
	[0, 0.16)	[0.16, 0.33)	[0.33,1]			2.5%	50%	97.5%
	0.656	0.249	0.095			0.169	0.156	0.035
0.589	0.269	0.141	0.198	0.185	0.037	0.136	0.812	
0.475	0.284	0.241	0.255	0.232	0.033	0.169	0.913	
0.428	0.269	0.303	0.288	0.256	0.029	0.192	0.945	
0.362	0.209	0.429	0.364	0.308	0.016	0.260	0.988	

Abbreviations: DLT=dose limiting toxicity; CCI; SD=standard deviation.

**Hypothetical on-Study Data Scenarios**

To illustrate the performance of the Bayesian model used to guide dose finding, hypothetical dose finding scenarios following the provisional dose levels specified in the protocol are displayed. In each case, the possible recommended dose that can be used in the next cohort of participants is shown. These recommended doses are determined using the model-based assessment of the risk of DLT in future participants, EWOC criteria and maximum amount of escalation allows. In practice, the dose recommended by the adaptive Bayesian logistic model may be regarded as guidance. The final recommendation will be based on overall safety profile and PK data.

Table 15 shows some hypothetical dose escalation data scenarios for this sub-study and the corresponding recommendations for the next dose. CCI

**Table 15. Data Scenarios, Next Dose Recommendation, and the Interval Probability of Target Toxicity and Overdosing at Next Dose**

Scenarios	CCI	Pr(TT) at Next Dose	Pr(OD) at Next Dose
1		0.246	0.066

090177e1a0f4f44c\Approved\Approved On: 14-Jun-2024 22:12 (GMT)

**Table 15. Data Scenarios, Next Dose Recommendation, and the Interval Probability of Target Toxicity and Overdosing at Next Dose**

Scenarios	CCI	Pr(TT) at Next Dose	Pr(OD) at Next Dose
2		0.357	0.170
3		0.348	0.186
4		0.376	0.137
5		0.445	0.205
6		0.336	0.112
7		0.161	0.178
8		0.458	0.077
9		0.493	0.184
10		0.478	0.028
11		0.402	0.231

CCI  
 Abbreviations: BID=twice daily; CCI  
 ; Pr(TT)=probability of target toxicity; Pr(OD)=probability of overdosing;  
 CCI

**Operating Characteristics**

A simulation study is used to illustrate the properties of the dose finding model guided by BLRM. Several example scenarios were investigated and in each scenario 1000 trials were simulated.

090177e1a0f4f44c\Approved\Approved On: 14-Jun-2024 22:12 (GMT)

**Simulation Scenarios**

Several scenarios are considered for this sub-study (Table 16). Scenario 1 represents the case when the distribution of DLT coincides with prior, ie, the true DLT probability equals to mean of prior DLT. Scenarios 2-3 represent an increase in DLT rate compared to Scenario 1.

**Table 16. Dose Limiting Toxicity Rate Scenarios**

Scenarios	CCI				
1. Mean prior DLT rate	0.169	0.198	0.255	0.288	0.364
2. 30% more toxic than the mean prior DLT rate	0.220	0.257	0.331	0.374	0.473
3. Higher dose is overly toxic	0.169	0.237	0.331	0.432	0.728

\* Nirogacestat dose is fixed at 100 mg BID.

Abbreviations: BID=twice daily; CCI

**Simulation Details**

Simulations were performed using R version 3.6.1 (The R-project for Statistical Computing, <https://www.r-project.org/>), and JAGS 4.3.0 to perform the MCMC analyses.

CCI

For this sub-study, the starting dose was elranatamab 4 mg (QW) and nirogacestat 100 mg BID. The maximum number of participants per trial was set to 30. The trial was stopped when the following criteria were met:

- At least 6 participants have been treated at the recommended MTD  $\tilde{d}$ .
- The dose  $\tilde{d}$  satisfies one of the following conditions:
  - The probability of target toxicity at dose  $\tilde{d}$  exceeds 50%, ie,  $\Pr(0.16 \leq \pi_{\tilde{d}} < 0.33) \geq 50\%$ ;
  - A minimum of 18 participants have been treated in the trial.

The following metrics were assessed in the simulations:

- Percentage of participants receiving dose combination(s) in the target toxicity interval;
- Percentage of participants receiving an overdose;

090177e1a0f4f44c\Approved\Approved On: 14-Jun-2024 22:12 (GMT)

- Percentage of participants receiving an under dose;
- Probability that recommended MTD at the end of the trial is in the target toxicity interval;
- Probability that recommended MTD is an overdose;
- Probability that recommended MTD is an under dose;
- Percentage of trials stopped without MTD declaration;
- Average sample size.

**Simulation Results**

Operating characteristics for this sub-study are presented in Table 17. The percentage of trials with a correctly identified MTD ranges from 48.0% to 89.6%. The average sample size is approximately 14 to 18 participants.

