**Table 2. Study Intervention Dose Levels and Administration**

Dose Levels (DL)	Elranatamab	Nirogacestat
1 (starting dose level)	Priming Dose: 4 mg C0D1 SC Full Dose: 4 mg C1D1 SC, weekly thereafter b	100 mg PO BID continuous starting on C1D1 until response a
2	2 Step-up Priming Dose: 4 mg C0D1 SC / 8 mg C0D4 SC Full Dose: 12 mg C1D1 SC, weekly thereafter b	100 mg PO BID continuous starting on C1D1 until response a
3	2 Step-up Priming Dose: 12 mg C0D1 SC / 32 mg C0D4 SC Full Dose: 32 mg C1D1 SC, weekly thereafter b	100 mg PO BID continuous starting on C1D1 until response a
Nirogacestat De-Escalation Levels		
3A	2 Step-up Priming Dose: 12 mg C0D1 SC / 32 mg C0D4 SC Full Dose: 32 mg C1D1 SC, weekly thereafter b	100 mg PO QD continuous starting on C1D1 until response a
4A	2 Step-up Priming Dose: 12 mg C0D1 SC / 32 mg C0D4 SC Full Dose: 76 mg C1D1 SC, weekly thereafter b,c	100 mg PO QD continuous starting on C1D1 until response a
3B	2 Step-up Priming Dose: 12 mg C0D1 SC / 32 mg C0D4 SC Full Dose: 32 mg C1D1 SC, weekly thereafter b	50 mg PO QD continuous starting on C1D1 until response a
4B	2 Step-up Priming Dose: 12 mg C0D1 SC / 32 mg C0D4 SC Full Dose: 76 mg C1D1 SC, weekly thereafter b,c	50 mg PO QD continuous starting on C1D1 until response a

- a. For Dose levels 3A/3B and 4A/4B, nirogacestat will be adjusted to 50 mg QD continuous at time of confirmed VGPR. Once CR (or better) is confirmed, nirogacestat will be permanently discontinued. For all other dose levels, nirogacestat can be continued or adjusted based on this guidance, per investigator discretion. See Section 6.1.1.5.
- b. Starting at Cycle 7, if a participant has received QW dosing for at least 6 cycles and PR or better persisting for ≥2 months, dose interval will be changed from QW to Q2W. See Schedule of Activities.
- c. For participants on Dose levels 4A and 4B receiving CCI dosing, CCI the dose interval will be changed to CCI

090177e1a0f4f44c\Approved\Approved On: 14-Jun-2024 22:12 (GMT)

CCI

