##### Assessment of Participant Risk

After each dosing cohort of participants completes the DLT observation period, the posterior distribution for the risk of DLT for each dose combination will be evaluated. The posterior distributions will be summarized to provide the posterior probability that the risk of DLT lies within the following intervals.

- Underdosing: [0, 0.16);
- Target toxicity: [0.16, 0.33);
- Excessive toxicity: [0.33, 1].

CCI

### 5.1.2.2. Phase 2

The Phase 2 part of this sub-study is designed to have an interim analysis for futility and a primary analysis. The interim analysis will be conducted after the first 25 participants are treated and followed for at least 2 post-baseline disease assessments in this sub-study. The primary analysis will be conducted once all participants have been followed for response for at least 6 months or have otherwise discontinued response assessments within the first 6 months of treatment.

Table 3 presents the operating characteristics of this 2-stage design, ie, the probability of early trial termination at the interim futility analysis and the probability of observing the critical number of objective responses (i.e.,  $\geq 38$  objective responses in 50 participants) at the primary analysis if the true ORR ranges from 65% to 90%. Specifically,

- If the true ORR = 65%, the probability of stopping the study due to futility at the interim analysis is 0.533, and the probability of observing critical number of responses at the primary analysis is 0.064.
- If the true ORR = 80%, the probability of stopping the study due to futility at the interim analysis is 0.047, and the probability of observing critical number of responses at the primary analysis is 0.806.

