**Table 17. Operating Characteristics**

Scenarios	Participant Allocation (%)			Prob of Declare MTD (%)			Prob of Stop with no MTD Found (%)	Average Sample Size
	UD	TT	OD	UD	TT	OD		
1. Mean prior DLT rate	24.1	75.9	0	4.3	89.6	0	6.1	18
2. 30% more toxic than the mean prior DLT rate	0	73.7	26.3	0	48.0	29.7	22.3	14
3. Higher dose is overly toxic	0	70.4	29.6	0	52.6	31.5	15.9	15

Abbreviations: MTD=maximum tolerated dose; OD=overdose; TT=target toxicity; UD=under dose.

**9.2. Appendix 2: BLRM Design** CCI

CCI

[figure not shown]
090177e1a0f4f44c\Approved\Approved On: 14-Jun-2024 22:12 (GMT)

**Table 188. Prior Distribution for the Model Parameters** CCI

Parameter	Mean	Standard deviations	Correlation
Elranatamab single agent parameters: CCI			
$(\log(\alpha_1), \log(\beta_1))$	CCI		
Nirogacestat single agent parameters: CCI			
$(\log(\alpha_2), \log(\beta_2))$	CCI		
Interaction parameter: Normal prior			
$\eta_{12}$	CCI		

$\eta_{12}$ : Two-way interaction between elranatamab and nirogacestat.

Abbreviations: CCI

**Table 19. Start of PA8 Data Scenarios, Next Dose Recommendation, and the Interval Probability of Target Toxicity and Overdosing at Next Dose**

Scenarios	CCI	Pr(TT) at Next Dose	Pr(OD) at Next Dose
1	CCI	0.295	0.030
		0.219	0.162
2		0.396	0.137
3		0.206	0.021
		0.209	0.145
4		0.294	0.2497
5		0.277	0.241

CCI; mg=milligrams;

Pr(TT)=probability of target toxicity; Pr(OD)=probability of overdosing.

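### The base-case row of the sub-study A dose-finding simulation reports under-dosing that its own scenario rules out, so the quoted 89.6% is unverified

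*SAP*

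**What the plan says.** Section 5.1.2.1 of the sub-study A SAP (Assessment of Participant Risk) sorts doses by true DLT risk. Under-dosing is given as "Underdosing: [0, 0.16", with the upper limit excluded. Target toxicity runs from 0.16 to below 0.33, and excessive toxicity is 0.33 or more. The stopping rule under Simulation Details in Appendix 1 uses the same two cut-points for the target interval.

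Appendix 1 then defines the base case: "Scenario 1 represents the case when the distribution of DLT coincides with prior, ie, the true DLT probability equals to mean of prior DLT". Table 16 lists the five true rates for each scenario, and its footnote says "Nirogacestat dose is fixed at 100 mg BID". Table 17 gives, for each scenario, the share of participants and the share of trials in the under-dose (UD), target (TT) and overdose (OD) classes. The Simulation Results text summarises: "The percentage of trials with a correctly identified MTD ranges from 48.0% to 89.6" per cent, with an average sample size of about 14 to 18.

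Master SAP section 5.1.2.1 and its Appendix 1 (Tables 14 and 15, and the results text) contain the same intervals, rates and results.

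**The concern.** The class of a dose depends only on its true DLT rate. If a scenario contains no dose below 0.16, no simulated participant can be under-dosed and no trial can declare an under-dosed MTD. The Scenario 1 row of Table 17 nevertheless shows non-zero entries in both under-dose cells. It also shows 0% overdose, although the top Scenario 1 rate lies in the excessive interval.

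Scenario 1 is the base case and the only source of the 89.6%. A reader using the table to judge how often the design finds the right dose, or how well it controls overdosing, cannot tell which Scenario 1 entries to trust.

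**Working it through.** **Inputs.** Cut-points 0.16 and 0.33 (SAP 5.1.2.1). True rates from Table 16, results from Table 17. 1000 trials per scenario (Operating Characteristics). Prior means and medians from Table 14 of the sub-study A SAP and Table 12 of the master SAP.

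**Step 1: classify each true rate.**

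| Scenario | True rates | Class |
|---|---|---|
| 1 | 0.169, 0.198, 0.255, 0.288, 0.364 | TT, TT, TT, TT, OD |
| 2 | 0.220, 0.257, 0.331, 0.374, 0.473 | TT, TT, OD, OD, OD |
| 3 | 0.169, 0.237, 0.331, 0.432, 0.728 | TT, TT, OD, OD, OD |

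**Step 2: compare with Table 17.**

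| Scenario | Participants UD / TT / OD (%) | MTD declared UD / TT / OD (%) | No MTD (%) | Mean N |
|---|---|---|---|---|
| 1 | 24.1 / 75.9 / 0 | 4.3 / 89.6 / 0 | 6.1 | 18 |
| 2 | 0 / 73.7 / 26.3 | 0 / 48.0 / 29.7 | 22.3 | 14 |
| 3 | 0 / 70.4 / 29.6 | 0 / 52.6 / 31.5 | 15.9 | 15 |

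No scenario has an under-dose level. Table 17 correctly shows UD 0 for Scenarios 2 and 3, but not for Scenario 1. Scenario 3 has the same lowest rate as Scenario 1 (0.169) and reports UD 0, so a different under-dose cut-off does not explain the row.

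**Step 3: is it a typing or extraction error?** The Scenario 1 row adds up: 24.1 + 75.9 + 0 = 100 and 4.3 + 89.6 + 0 + 6.1 = 100. It is identical in both SAPs. A single wrong digit would break the sums.

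**Step 4: are the Table 16 rates misprinted?** The Scenario 1 rates equal the Mean column of the prior table. Multiplying them by 1.3 gives 0.2197, 0.2574, 0.3315, 0.3744 and 0.4732, which match the printed Scenario 2 rates within rounding. The printed rates therefore agree with the scenario definition.

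**Step 5: size.**
- Participants: 24.1% × 18 = 4.3 per trial.
- Trials: 4.3% × 1000 = 43. Among trials that declare an MTD, 4.3 / (4.3 + 89.6) = 4.6%.
- Setting the two cells to 0 and changing nothing else leaves row totals of 75.9 and 89.6 + 6.1 = 95.7, so the row needs more than a deletion.

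**Step 6: what the row would become under three possible causes.**

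| Possible cause | Participants UD / TT / OD (%) | MTD UD / TT / OD (%) | Effect on the quoted range |
|---|---|---|---|
| UD and OD columns swapped | 0 / 75.9 / 24.1 | 0 / 89.6 / 4.3 | 89.6% stands; base-case overdose is no longer 0 |
| Target doses counted as UD | 0 / 100 / 0 | 0 / 93.9 / 0 | 48.0% to 93.9% |
| Other rates simulated | not derivable | not derivable | whole row unsupported |

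In the first two cases the 6.1% and the mean sample size of 18 are unchanged. As an example of the third, the prior medians (0.122, 0.136, 0.169, 0.192, 0.260) classify as UD, UD, TT, TT, TT, which fits the printed pattern of UD above 0 and OD 0. That is an inference, not proof.

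**Step 7: the 0% overdose entry.** Assume 3 participants per level (range 2 to 4; the escalation details are redacted). The chance of no DLT through the four lower Scenario 1 levels is (0.831 × 0.802 × 0.745 × 0.712)³ = 4.4%, or about 44 of 1000 trials (12.5% to 1.6% over the range). Some simulated trials would therefore be expected to have a clear path to the top dose. Redacted rules could still block it, so this is supporting evidence only.

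**The case against.** The strongest reply is that the cells must be 0 only if the Table 16 rates were the ones simulated. If other rates were run, the under-dose cells may report that run correctly, and the mislabelling lies in Table 16. It is true that the documents cannot show what was run. But the SAP defines Scenario 1 as the prior mean, and Table 16 matches that definition, so the row is wrong for the scenario as specified. Rerunning at the printed rates resolves this case too.

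A second reply is that the three causes are not equally likely. Every simulated trial begins at one level: "For this sub-study, the starting dose was elranatamab 4 mg (QW) and nirogacestat 100 mg BID". With starting cohorts of 3 or 4 (assumed; range 2 to 6), that level alone takes 3/18 = 17% to 4/18 = 22% of participants (11% to 33%), close to the printed 24.1%. This favours target doses counted as under-doses, in which case the SAP understates its performance. The point is fair, but it rests on redacted details and settles nothing.

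A third reply is that nothing depends on the row. This largely stands. The simulation is presented as illustrative. Dosing uses the posterior from accrued data together with other evidence, and no sample size or boundary is taken from this table. The simulation also covers only nirogacestat 100 mg BID, whereas Table 2 of the sub-study A SAP ("Study Intervention Dose Levels and Administration") now lists three BID and four QD levels. These facts limit the severity; they do not make the row consistent.

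**Conclusion.** The Scenario 1 row is wrong as written. Given the Table 16 rates and the 0.16 cut-off, the under-dose entries must be exactly 0, not 24.1% of participants and 4.3% of trials. Simulation error cannot account for the difference, because the class of each dose is fixed in advance.

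The 89.6% upper end is unverified rather than shown to be wrong: it stands under a column swap, becomes 93.9% if target doses were misclassified, and has no support if other rates were simulated. The conclusion assumes only that Scenario 1 is what the SAP says it is. The error affects stated operating characteristics and no dosing decision, so it is a reporting correction of low severity that should still be made.

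**What to change.** Retrieve the stored Scenario 1 output and compare it with Tables 16 and 17. If the columns were mis-tabulated, correct them. If other rates were used, rerun Scenario 1 at the printed Table 16 rates. Then restate the Scenario 1 row and, where they change, the 48.0% to 89.6% range and the 14 to 18 sample-size range. Make the same changes in the sub-study A SAP (Table 17 and Simulation Results) and the master SAP (Table 15 and Simulation Results).

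The cost is one check of stored output or one simulation run, plus a few restated figures in two documents. The figures may move in either direction.

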**Table 17. Operating Characteristics**

Scenarios	Participant Allocation (%)			Prob of Declare MTD (%)			Prob of Stop with no MTD Found (%)	Average Sample Size
	UD	TT	OD	UD	TT	OD		
1. Mean prior DLT rate	24.1	75.9	0	4.3	89.6	0	6.1	18
2. 30% more toxic than the mean prior DLT rate	0	73.7	26.3	0	48.0	29.7	22.3	14
3. Higher dose is overly toxic	0	70.4	29.6	0	52.6	31.5	15.9	15

Abbreviations: MTD=maximum tolerated dose; OD=overdose; TT=target toxicity; UD=under dose.

**9.2. Appendix 2: BLRM Design** CCI

CCI

[figure not shown]
090177e1a0f4f44c\Approved\Approved On: 14-Jun-2024 22:12 (GMT)

**Table 188. Prior Distribution for the Model Parameters** CCI

Parameter	Mean	Standard deviations	Correlation
Elranatamab single agent parameters: CCI			
$(\log(\alpha_1), \log(\beta_1))$	CCI		
Nirogacestat single agent parameters: CCI			
$(\log(\alpha_2), \log(\beta_2))$	CCI		
Interaction parameter: Normal prior			
$\eta_{12}$	CCI		

$\eta_{12}$ : Two-way interaction between elranatamab and nirogacestat.

Abbreviations: CCI

**Table 19. Start of PA8 Data Scenarios, Next Dose Recommendation, and the Interval Probability of Target Toxicity and Overdosing at Next Dose**

Scenarios	CCI	Pr(TT) at Next Dose	Pr(OD) at Next Dose
1	CCI	0.295	0.030
		0.219	0.162
2		0.396	0.137
3		0.206	0.021
		0.209	0.145
4		0.294	0.2497
5		0.277	0.241

CCI; mg=milligrams;

Pr(TT)=probability of target toxicity; Pr(OD)=probability of overdosing.

**9.3. Appendix 3: List of Abbreviations**

Abbreviation	Term
ADA	anti-drug antibody
ADC	antibody-drug conjugate
AE	adverse event
AESI	adverse events of special interest
ALP	alkaline phosphatase
ALT	alanine aminotransferase
AST	aspartate aminotransferase
ASTCT	American Society for Transplantation and Cellular Therapy
ATC	anatomic Therapeutic Chemical
AUC	area under the curve
AUC last	area under the plasma concentration-time profile from time zero to the time of the last quantifiable concentration (C last )
BCMA	B-cell maturation antigen
BLQ	below the limit of quantitation
BLRM	Bayesian logistic regression model
BMA	bone marrow aspirate
BMI	body mass index
BOR	best overall response
BP	blood pressure
CRR	complete response rate
CI	confidence interval
C max	maximum observed concentration
CR	complete response
CRF	case report form
CRS	cytokine release syndrome
CSR	clinical study report
CTC	Common Toxicity Criteria
CTCAE	Common Terminology Criteria for Adverse Events
CV	Coefficient of variation
DI	dose intensity
DLT	dose limiting toxicity
DOCR	duration of complete response
DOMRD	duration of minimal residual disease
DOR	duration of response
ECG	electrocardiogram
ECHO	echocardiogram
ECOG	Eastern Cooperative Oncology Group
eCRF	electronic case report form
eDISH	evaluation of drug-induced serious hepatotoxicity
EMD	extramedullary disease

090177e1a0f4f44c\Approved\Approved On: 14-Jun-2024 22:12 (GMT)

Abbreviation	Term
EORTC MY20	European Organization for Research and Treatment of Cancer Multiple Myeloma module
EORTC QLQ-C30	European Organization for Research and Treatment of Cancer Quality of Life of Cancer Patients core module
EOS	end of study
EOT	end of treatment
ICANS	immune cell-associated neurotoxicity syndrome
IMWG	International Myeloma Working Group
irAE	immune-related adverse event
IRT	interactive response technology
LLN	lower limit of normal
LLOQ	lower limit of quantitation
MRD	minimal residual disease
MUGA	multigated acquisition
N/A; NA	not applicable; not assessed
NAb	neutralizing antibody
NCI	National Cancer Institute
NE	not evaluable
ORR	objective response rate
OS	overall survival
OTR	outside toxicity reference
PD	progressive disease
PFS	progression-free survival
PGIC	Patient Global Impression of Change
PGIS	Patient Global Impression of Severity
PI	proteasome inhibitor
PK	pharmacokinetic(s)
PR	partial response
PRO	patient-reported outcome
PT	preferred term
QoL	quality of life
QT	time from the beginning of the QRS complex to the end of the T wave
QTc	corrected QT
QTcF	corrected QT (Fridericia's method)
RDI	relative dose intensity
RP2D	recommended phase 2 dose
RRMM	relapsed/refractory multiple myeloma
SAE	serious adverse event
SAP	statistical analysis plan
sCR	stringent complete response
SD	stable disease
sMRD	sustained minimal residual disease

Abbreviation	Term
SMQ	Standardised MedDRA Queries
SOC	system organ class
TBILI	total bilirubin
TEAE	treatment-emergent adverse events
T max	time for C max
TTR	time to response
ULN	upper limit of normal
VGPR	very good partial response
WBC	white blood cell
WHO	World Health Organization

**Protocol C1071004  
(MAGNETISMM-4)**

